6.3. Precautions

All hazards associated with the use of the Certus system have been identified and appropriately mitigated. Design considerations were taken to reduce the risks associated with existing MW ablation systems, including improved system usability and cable management.

Important: Probe temperatures are highly dependent on tissue variables such as perfusion and vasculature. Probe temperatures are likely to vary from procedure to procedure based on these tissue variables. These temperature variations do not, by themselves, indicate a malfunctioning probe or system.

Electrosurgical/electrocautery devices may interfere with the Certus system and cause system errors. Ensure that all Certus probes are removed from the patient prior to using electrosurgical/electrocautery devices.

Use only Certus Ablation Probes from NeuWave Medical with the Certus Ablation System. Probes from other manufacturers may cause patient injury or fail to function properly.

The Certus system uses a CO₂ cooling system where all other MW systems use sterile water, but the risks associated with this cooling system do not differ from the risks inherent in cryogenic ablation systems, also widely accepted in clinical use. Thus, the Certus system does not introduce new hazards or intended uses.

This product should only be used by clinicians and staff properly trained in the use of the technology and its associated warnings and cautions.

Refer to the Certus Microwave Ablation System and Accessories accompanying documents for a complete and comprehensive list of Warnings and Cautions.

Confidential Page 25 of 61

7. OVERALL DESIGN

7.1. Trial Design

This is a single-arm, prospective, multicenter study. Individuals who are assessed for MW ablation of HCC in accordance with their institution's standard-of-care (SOC), who meet study entry criteria and sign the informed consent will be enrolled. The patients will be treated with MW ablation and afterwards will be followed for up to 36 months after the ablation procedure to assess safety and ablation outcomes. In addition to the final analysis after all enrolled patients complete the 36-month observation period, a summary of selected endpoints will be provided after all enrolled patients have completed each of the 1-month and 12-month visits.

7.1.1. Trial Objective

The key objective of this study is to evaluate the efficacy and safety of the NeuWave Certus Microwave Ablation System in the treatment of Chinese patients with a single HCC tumor of up to 5 cm or a maximum of 3 HCC tumors of up to 3 cm per tumor.

7.1.2. Trial Endpoints

Efficacy Endpoints

The efficacy endpoints are defined, as follows:

- Technical Success, defined as a combination of A0 ablations (complete tumor ablation with a surrounding 5 mm margin) and A1 ablations (complete tumor ablation with inadequate margins) based on contrast-enhanced MRI performed up to 7 days following the original ablation procedure.
- Technical Efficacy, defined as a combination of A0 ablations (complete tumor ablation with a surrounding 5 mm margin) and A1 ablations (complete tumor ablation with inadequate margins), based on contrast-enhanced MRI scans at 1 month (+/- 7 days) after the original ablation procedure.
- Local tumor progression (LTP), evaluated at every visit after the ablation of the target tumor(s). LTP describes the appearance of tumor foci at the edge of the ablation zone, after at least one contrast-enhanced follow-up MRI scan has documented adequate ablation and an absence of viable tissue in the target tumor and surrounding ablation margin by using imaging criteria.
- Secondary efficacy rate, defined as the percentage of tumors that have undergone successful repeat ablation following identification of local tumor progression at any time during study follow up.
- Progression-free survival, defined as length of time from the original ablation procedure until any type of disease progression (i.e. local or distant).
- Overall survival measured from the time of the original ablation procedure to the time of death or last follow-up if death has not occurred.

Confidential Page 26 of 61

Safety Endpoint

The safety endpoint is the rate of AEs and SAEs reported at each analysis and cumulatively throughout the entire study period.

Patient Reported Outcomes:

- Pain, as measured by Numeric Pain Rating Scale, before the ablation procedure (measured at Screening Visit), post ablation (within 7 days after ablation]), and at the 1-month follow-up visit.
- Quality of Life, as measured by EORTC QLQ-C30 and liver-specific EORTC QLQ-HCC18, before the ablation procedure (measured at Screening Visit), post ablation (within 7 days after ablation), and at each follow-up visit.

Health Economics:

 Health economics associated with the ablation procedure, including complete procedure time, ablation time, number of ablations, number and types of probes, change in probe position, number of computed tomography (CT) and ultrasound scans performed for probe and margin assessment, and length of hospital stay.

7.1.3. Trial Method Selection and Its Rationale

This is a single-arm, prospective study. As such, there is no randomization or control groups. Individuals who are assessed for MW ablation of HCC in accordance with their institution's standard of care (SOC), who meet study entry criteria and sign the informed consent will be enrolled. Because it is a prospective study, selection bias may be reduced.

7.1.4. Measures to Reduce and Avoid Bias

There will be no central reviewer, however, all MRI scans and the ultrasound video taken on the day of ablation should be sent to the Sponsor.

The study related data will be recorded in the original Medical Records and reviewed during the monitoring process. Proper Training for the investigators will be planned to ensure all investigators have equal adequate experience with the device prior to commencing enrollment at their site. In addition, all sites will treat a minimum of 3 patients each, as part of the roll-in phase, which will only be included in the safety set. This is intended to reduce any operational bias due to learning curve.

The investigator should communicate further with the patients to improve the patient compliance. This will help to reduce the informational bias.

Confidential Page 27 of 61

7.1.5. Selection of Patients

1) Inclusion criteria

- Diagnosed primary or recurrent HCC determined in accordance with the institution's SOC procedure, single tumor size up to 5 cm or a maximum of 3 tumors up to 3 cm per tumor. Tumor size must be measured with at least 2-dimensional (2D) imaging.
- Scheduled for MW ablation of the liver.
- Performance status 0-2 (Eastern Cooperative Oncology Group classification).
- Functional hepatic reserve based on the Child-Pugh score (Class A or B).
- Give voluntary, written informed consent to participate in this study and willing to comply with the study-related evaluation and procedure schedule.
- At least 18 years of age.

2) Exclusion criteria

- ASA score ≥ 4.
- Active bacterial or fungal infections which are clinically significantly.
- Chemotherapy or radiation therapy for HCC performed within 30 days prior to the study procedure.
- Patient with implantable pacemakers or other electronic implants.
- Planned/ scheduled liver surgery.
- Platelet count ≤ 50 × 10⁹/L.
- Patients with uncorrectable coagulopathy at time of screening based on investigator judgement. Severe blood coagulation dysfunction (bleeding tendency, prothrombin time [PT] was greater than normal control for 3~5 seconds, platelet count [PLT] was less than 50x10⁹/L, and the international normalized ratio (INR) was greater than 1.5).
- Patient with renal failure and on renal dialysis.
- Scheduled concurrent procedure other than MW ablation in the liver.
- Pregnant or breast feeding.
- Physical or psychological condition which would impair study participation.
- Participation in any other interventional clinical study within 1 month before screening and concurrently during the study.
- The patient is judged unsuitable for study participation by the investigator for any other reason.

3) Criteria of Sponsor's Discontinuation of the Trial

The Sponsor has the right to terminate the study early for a single site, multiple sites or all sites temporarily or permanently. Reasons may include, but are not limited to: safety issue or ethical issue, inaccurate or incomplete data record, non-compliance or dissatisfactory quality or quantity of the recruited patients. Health authorities also have the right to terminate a study.

Confidential Page 28 of 61

This study does not require a Data Safety Monitoring Board.

Other criteria:

Patients may be withdrawn if any of the following complications or adverse situations occur:

- The patient experiences a major complication, which is defined as an event that leads
 to substantial morbidity and disability (e.g., results in the unexpected loss of an organ)
 that increases the level of care, or results in hospital admission, or substantially
 lengthens the hospital stay (Society of Interventional Radiology [SIR] classifications C
 to E).
- The patient requires a blood transfusion or interventional drainage procedure.

Flow of Sponsor's Discontinuation of the Trial:

If this study is terminated or discontinued early, the Sponsor or its representative will inform the investigator/affiliated unit and regulatory authority of the termination of the study and the reasons for the termination or discontinuation, according to the applicable requirements. The Sponsor or investigator/affiliated unit should also inform ECs and include the reasons for termination or discontinuation, according to the applicable requirements. In addition, all unused study devices and other study materials should be returned according to the Sponsor's study procedures.

Study/treatment termination and patient discontinuation criteria and procedures

In accordance with the current revision of the Declaration of Helsinki, a patient has the right to withdraw from the study at any time for any reason without prejudice to their future medical care by the physician or the institution. Should a patient (or patient's legally authorized guardian/representative) decide to withdraw, 1) all data collected up to the point of withdrawal will be considered for analysis; and 2) all efforts will be made to collect and report the final visit observations as thoroughly and timely as possible. The primary reason for early withdrawal will be recorded on the electronic case report form (eCRF). The criteria for withdrawal of patients from the study include, but are not limited to, the following:

Withdrawal of consent: Any method of contact with the patient in which the patient's states that he or she no longer wants to participate in the study-specific activities constitutes withdrawal of consent from participation in the study. This decision must be "self-determination" and should be documented in the eCRF; or, the investigator may determine the withdrawal of patients from the study according to reasonable medical judgement;

Adverse event: The AE or SAE may not cause the patients to discontinue the study. If the investigator decides to withdraw a patient from the study, this patient must be followed up, until the AE is resolved or until the stable clinical endpoint is reached;

Death: The cause of death will be documented.

Lost-to-follow-up: All patients should be able to participate in all scheduled clinical follow-ups, providing the appropriate contact information. If a patient can't return to undergo the scheduled

Confidential Page 29 of 61

clinical visit, attempts to contact the patient by phone should be done for 3 times to ask the patient to participate in all scheduled clinical follow-ups. Each attempt to contact should be recorded in the source document. If the patient makes no response to all three times of telephone contact, the investigator must send a registered mail to the patient. If the patient makes no response to the registered mail and makes no further contact, the patient is considered lost-to-follow-up and the respective eCRF will be completed.

Procedure for Patient's Discontinuation from the Study:

The patients must return for all follow-up visits as specified at the end of the synopsis in Table 1: Schedule of Activities. If the patient is withdrawn from the study early, the reasons for termination will be documented in the source document and site files and submitted via the eCRF.

Patients withdrawn from the study early will be included in the analysis of results, however, no new patients will be recruited to replace the patients withdrawn from the study as a 20% attrition rate has already been considered in the current sample size.

4) Enrollment

Patients will be considered enrolled into the study upon satisfaction of the following criteria:

- Completion of the informed consent process.
- It is determined by the investigator that the patient meets all inclusion criteria and does not meet any exclusion criteria.

No procedures related to the study and which are not SOC should be conducted prior to signing the informed consent.

5) Expected overall duration of clinical trial and reasons for determination

The expected overall duration is approximately 65 months, including the time that each site's Ethics Committee takes to approve the trial protocol, institution contract sign-off, Human Genetic Material Office approval, duration of patient enrollment, duration of follow-up, time for data management, statistical analysis, and time to write, review and approve the clinical study report.

6) Expected duration of participation of each patient

The duration of each patient's participation in the study will be around 37 months (about 1 month for Screening and 36 months for follow-up). The follow-up schedule will be based on the original ablation procedure date. A re-ablation for any reason will not change or extend the follow-up visit schedule.

7) Number of patients required for clinical trial

This study will include 137 patients, of which 3 patients per site (n=12) will be part of the runin phase. This is a single-arm study, and hence there will be no randomization of patients. See Section 8.2 "Calculation of Sample Size" for the basis for selecting this sample size.

Confidential Page 30 of 61

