7.1.7. Safety Evaluation Method

1) Description of safety parameters

The safety parameters in this study are all AEs and SAEs for 30 days after any ablation procedure (original or additional); after 30 days post an ablation procedure through the end of the study, only SAEs will be reported and assessed. The safety endpoint is the rate of AEs and SAEs reported at each analysis and cumulatively throughout the entire study period.

2) Selection of method and time to evaluate, record, and analyze the safety parameters

Confidential Page 31 of 61

NeuWave Medical, Inc. NEU_2017_07

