The number and percentage of tumors achieving Technical Success will be summarized and a 95% confidence interval will be estimated. Technical Success will be evaluated based on the margin achieved after the first ablation and prior to any repeat ablations within the first 7 days.

A similar summary will be provided for Technical Efficacy. This endpoint will be based on the scan obtained at Visit 3 and will count as successes patients with A0 or A1 margins in that scan and who did not have an A2 margin since the Visit 2B scan. Additionally, if a patient received a repeat ablation for correcting a margin (to go from A1 to A0) within the first 30 days, this will also count as a success. Patients with repeat ablations to correct an A2 margin from Visit 2B to Visit 3 will not count as success for Technical Efficacy. The number and percentage of tumors with A0 and A1 margins will be presented as a subcategorization within each presentation of Technical Success and Technical Efficacy, as well as a summarization for the number and reasons for repeat ablations through Visit 3.

Local tumor progression rates at 1, 3, 6, 9, 12, 18, 24, 30, and 36 months will be estimated using the Kaplan-Meier method and 95% confidence intervals will be provided. Any repeat ablation required after Visit 3 (Month 1) will be identified as an instance of local tumor progression. A similar summary will be provided for the 36-month overall and progression-free survival rates.

Confidential Page 41 of 61

The number and percentage of patients experiencing AEs will be summarized at the preferred term level using the Society of Interventional Radiology (SIR) clinical practice guidelines for event categorization. A similar summary will also be provided for device-related AEs, procedure-related AEs, all SAEs, device-related SAEs, and procedure-related SAEs. Adverse event rates will also be estimated using cumulative patient years of exposure as the denominator as well as total number of patient ablations.

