10. FEASIBILITY ANALYSIS

10.1. Likelihood Analysis of Success

The Certus Microwave Ablation System and Accessories have been cleared by the United States (US) Food and Drug Administration (FDA) and has been in clinical use since 2011 in the United States. The growing popularity of the Certus Microwave Ablation System result from

Confidential Page 43 of 61

its low risks of complications and high effectiveness in ablating tumors of the liver, lung, and kidney. Pre-clinical and clinical data has shown that MW ablation is safe and effective in liver tumors with low complication rates, high rates of technical success, lower rates of local tumor progression and promising disease-free and overall survival rates than have historically been reported for radiofrequency (RF).⁷

The largest clinical experience using MW ablation to treat HCC comes from China, in part due to early adoption of MW ablation systems available in Asia. That multicenter study of 1007 patients with primary liver cancer showed a technical success of 97.1% (1276/1363) and a local tumor progression rate of 5.9% (78/1363) with a mean follow-up time of 17.3 months (range, 3 to 68.9 months). The 1-, 3- and 5-year overall survival rates were 91.2%, 72.5% and 59.8%, respectively.⁵

Adoption of MW ablation systems has previously been limited by technical problems associated with suboptimal power handling, large antenna diameter, antenna shaft heating and unpredictable heating patterns. Despite these limitations, the results of clinical MW ablation studies have historically compared favorably with those of RF ablation. In recent years, MW ablation systems have advanced. The Certus Microwave Ablation System is a high-powered, gas-cooled, multiple antenna-capable MW device, allowing physicians to realize the theoretical heating advantages of MW energy compared with other ablation modalities.

Microwave ablation of HCC treatment is a minimally invasive procedure that may be performed in an outpatient setting and generally takes less than 2 hours for preparation and treatment. The patient is required to return to his or her study site for 9 follow-up visits over the course of 3 years or until early discontinuation for reasons such as (but not limited to) withdrawal of consent, physician decision to withdraw the patient, lost to follow up, or death.

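### Protocol 7.1.5 permits withdrawal after a major complication, transfusion or drainage, and nothing requires new SAEs, scheduled MRI or vital status to be collected once the triggering event has settled

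*Protocol*

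**What the plan says.** Under the sponsor's discontinuation criteria in Protocol 7.1.5, a paragraph of other criteria says "Patients may be withdrawn if any of the following complications or adverse situations occur". The first trigger is a major complication, SIR class C to E. The second is "The patient requires a blood transfusion or interventional drainage procedure".

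What happens next is spread over several places:

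- **Adverse-event paragraph of 7.1.5.** It opens with "The AE or SAE may not cause the patients to discontinue the study". It then lets the investigator withdraw the patient, in which case "this patient must be followed up, until the AE is resolved or until the stable clinical endpoint is reached".
- **Discontinuation procedure in 7.1.5.** It says "The patients must return for all follow-up visits as specified at the end of the synopsis". The next sentence, on patients withdrawn early, asks only that the reasons be documented and submitted.
- **Section 10.1.** The nine follow-up visits run for three years "or until early discontinuation for reasons such as (but not limited to) withdrawal of consent, physician decision to withdraw the patient".
- **Sections 7.2.4 and 14.4.** SAEs are reported through the end of the study. Neither section says whether this binds withdrawn patients.

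The endpoints at stake are cumulative. Section 7.1.7 says "The safety endpoint is the rate of AEs and SAEs reported at each analysis and cumulatively throughout the entire study period", and section 8.1 adds that adverse "event rates will also be estimated using cumulative patient years of exposure as the denominator". Protocol 8.6 and SAP 8.7 allow no imputation for early terminated patients. For patients without an event, Protocol 8.6 censors at the last known visit in the final analysis, whereas SAP 8.4.1 censors OS at the cut-off date when no death is reported.

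**The concern.** The withdrawal triggers are outcomes that a device safety study is meant to observe. Nowhere does the plan separate ending study ablation from ending data collection. A patient who has a serious procedural complication can therefore leave follow-up because of it. If such patients later have more SAEs, progressions or deaths than the others, the loss is informative.

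Complete follow-up carries weight here. The study is single-arm and supports registration in China (Protocol 4.3). It has no acceptance threshold, and performance is to be judged from all the data collected (Protocol 8.4). SAE reporting cannot stand in for vital status either, because death from progressive disease is not reported as an SAE (Protocol 14.2, notes).

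**Working it through.** **1. The plan's own figure.** 100/(1 - 0.20) = 125, plus 3 x 4 = 12 run-in patients, gives 137. This reproduces Protocol 8.2.1.

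**2. Patients exposed.** The protocol cites major complication rates for microwave ablation of 3.8% (10.2) and 5.9% (4.1.2).

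- Main phase: 125 x 0.038 = 4.8; 125 x 0.059 = 7.4. About 5 to 7.
- Safety Set: 137 x 0.038 = 5.2; 137 x 0.059 = 8.1. About 5 to 8.
- Transfusion or drainage only: no rate is given, so the number is unknown.

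**3. Follow-up lost if all m = 5 or 7 leave just after the month-1 visit** (an assumption, before other attrition).

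- Patient-years: 5 x 35/12 = 14.6 and 7 x 35/12 = 20.4, of 125 x 3 = 375. That is 3.9% and 5.4%.
- Follow-up MRIs: 8 of the 9 scans at Visits 3 to 11 for each patient, so 40 and 56 of 9 x 125 = 1,125. That is 3.6% and 5.0%.

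**4. Percentage of patients with any SAE.** Under Protocol 14.2, an event requiring in-patient or prolonged hospitalisation is an SAE, so most triggering events count. The patient is already in the numerator and stays in the FAS or SAF denominator (SAP 8.5.1). A later SAE cannot change that patient's any-SAE status. Only further preferred terms, or related events not already counted, can be missed.

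**5. Cumulative SAE rate per patient-year (Protocol 8.1).** Assume one triggering SAE per withdrawn patient, a rate r of 0.05 to 0.2 SAEs per patient-year in the others, and a later rate of k x r in those withdrawn.

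- SAEs captured: A = m + 3r(125 - m) + rm/12
- Observed rate: A/(375 - 35m/12)
- Rate with full follow-up: (A + k x r x 35m/12)/375

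Example with m = 7, r = 0.05, k = 1: A = 7 + 17.7 + 0.03 = 24.73. Observed 24.73/354.58 = 0.0697; full 25.75/375 = 0.0687; shift +1.6%.

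Example with m = 7, r = 0.2, k = 3: A = 77.92. Observed 77.92/354.58 = 0.2197; full 90.17/375 = 0.2404; shift -8.6%.

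| m | r | k = 1 | k = 2 | k = 3 |
|---|---|---|---|---|
| 5 | 0.05 | +0.9% | -2.2% | -5.0% |
| 5 | 0.2 | +0.3% | -3.3% | -6.6% |
| 7 | 0.05 | +1.6% | -2.3% | -5.9% |
| 7 | 0.2 | +0.5% | -4.3% | -8.6% |

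The shift is zero at k = A/[r(375 - 35m/12)], which is about 1.07 to 1.39. Below that, the retained triggering SAE over a shorter denominator pushes the rate up.

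**6. 36-month OS.** Take 72.5% in the others (the 3-year figure cited in Protocol 4.1.1), true OS s in those withdrawn, deaths after withdrawal not captured, and f = 5/125 = 0.040 or 7/125 = 0.056.

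- Last-visit censoring (Protocol 8.6): overstatement = f(0.725 - s)
- Cut-off censoring (SAP 8.4.1): overstatement = f(1 - s), because uncaptured deaths count as survival

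| s | Last visit, points | Cut-off, points |
|---|---|---|
| 0.725 | 0 | 1.1 to 1.5 |
| 0.50 | 0.9 to 1.3 | 2.0 to 2.8 |
| 0.30 | 1.7 to 2.4 | 2.8 to 3.9 |

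For scale, the 95% half-width is 1.96 x sqrt(0.725 x 0.275/125) = 7.8 points.

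**The case against.** The clause is permissive, and nothing suggests that it will be used routinely. The adverse-event paragraph can be read as leaning towards retention, the instruction to return for all visits sits under the discontinuation heading, and SAE reporting to the end of the study carries no stated exception for withdrawn patients. The triggering event is followed to resolution or stability (7.1.5, 14.4). When the patient chooses to withdraw, all efforts are made to obtain final-visit observations. Withdrawn patients stay in the analysis, and SAP 8.2 tabulates the reasons for discontinuation. The main safety summary is a percentage of patients, which is nearly immune, and the SAP's list of AE outputs contains no patient-year rate. No hypothesis or stopping rule depends on the result.

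Most of this stands, and it limits the size of the problem. It does not close the gap:

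- If "The AE or SAE may not cause the patients to discontinue the study" means must not, it conflicts with the withdrawal clause and with its own next sentence. If it means need not, it protects nothing.
- The return-for-visits line does not say that it covers withdrawn patients, and section 10.1 ends visits at physician withdrawal.
- Following the triggering event does not capture new SAEs, scheduled MRI or later deaths.
- Tabulated reasons show the loss but cannot recover the data.

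**Conclusion.** The point holds as a modest defect that is cheap to correct. The protocol lets follow-up end because of a procedural safety outcome, and it does not require new SAEs, scheduled MRI (hence LTP and PFS) or vital status to be collected afterwards. About 5 to 7 of 125 main-phase patients are exposed at the cited rates, plus an unknown number with transfusion or drainage only.

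The figures assume that every exposed patient is withdrawn at month 1; if only some are, the effects shrink roughly in proportion. The later SAE rates and the survival of withdrawn patients are assumptions, since the documents neither show nor exclude that these patients do worse.

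Three stronger readings are tempting, and the documents do not support them:

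- **That the complication itself goes unrecorded, or that the patient leaves the analysis.** It is recorded and followed, and data up to withdrawal are kept.
- **That the SAE rate is necessarily understated.** It rises slightly at equal later risk and falls only once later risk exceeds about 1.07 to 1.39 times that of the others.
- **That OS would be badly distorted.** Under the protocol's censoring the overstatement is 0 to about 2.4 points for true OS from equal down to 30%. The SAP cut-off rule makes it larger, and above zero even at equal survival, but that excess comes from the censoring rule, which is a separate matter. All the OS shifts in the table lie inside the 7.8-point half-width.

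**What to change.** In Protocol 7.1.5, state that a major complication, transfusion or interventional drainage may end further study ablation but does not end follow-up. SAEs, scheduled imaging where feasible and vital status are then collected to month 36 unless the patient withdraws consent. Reword the adverse-event paragraph to say that an AE or SAE does not by itself cause discontinuation. Align section 10.1 so that a physician's decision to stop study treatment does not end the visits.

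The cost is a short protocol clarification and continued visits, already scheduled in Table 1, for about 5 to 8 of 137 patients at the cited rates, plus any with transfusion or drainage only. Visit funding is set in contracts that are not part of these documents (Protocol section 17), so its effect cannot be priced here.
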